12.5.1.5 Risks Due to MRI

People are at risk for injury from the MRI magnet if they have some kinds of metal in their body.

People with fear of confined spaces may become anxious during an MRI. Those with back problems may have back pain or discomfort from lying in the scanner. The noise from the scanner is loud enough to damage hearing, especially in people who already have hearing loss. Everyone having a research MRI scan will be fitted with hearing protection.

There are no known long-term risks of MRI scans.

12.5.1.6 Risks Due to Gadolinium as a Contrast Agent in MRI

During part of the MRI, people receive gadolinium, a contrast agent, through an intravenous (IV) catheter (small tube). It will be done for research purposes.

The risks of an IV catheter include bleeding, infection, or inflammation of the skin and vein with pain and swelling.

Mild symptoms from gadolinium infusion occur in fewer than 1% of those who receive it and usually go away quickly. Mild symptoms may include coldness in the arm during the injection, a metallic taste, headache, and nausea. The risks due to gadolinium have been explained in detail in the consent document.

12.5.1.7 Risks Due to EKG

Other than possibly experiencing some minor skin irritation from the electrodes there are no anticipated risks related to complete the electrocardiogram

12.5.1.8 Blood Sampling Risks

Risks of blood draws include pain and bruising in the area where the needle is placed, lightheadedness, and rarely, fainting. When large amounts of blood are collected, low red blood cell count (anemia) can develop.

12.5.1.9 Non-Physical Risks of Genetic Research

- Risk of receiving unwanted information: Anxiety and stress may arise as a result of the anticipation that unwanted information regarding disease related DNA sequencing or disease tendencies, or misattributed paternity. Participants will be clearly informed that the data related to DNA sequencing and genetic analysis is coded, investigational and will not be shared with participants, family members or health care providers.
- Risk related to possibility that information may be released: This includes the risk that data related to genotype, DNA sequencing or risk for disease tendency or trait can be released to members of the public, insurers, employers, or law enforcement agencies. Although there are no plans to release results to the participants, family members or health care providers, this risk will be included in the informed consent document.
- Risk to family or relatives: Family members or relatives may or may not want to be aware of familial tendencies or genetic risks of disease which may cause anxiety about possible future health problems. As previously noted, participants will be notified of any medically significant and actionable incidental findings. Study results will not be shared with participants.

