5.4.3 Management of Results

Subjects will be contacted if a clinically actionable gene variant is discovered. Clinically actionable findings for the purpose of this study are defined as disorders appearing in the American College of Medical Genetics and Genomics recommendations for the return of incidental findings that is current at the time of primary analysis. (A list of current guidelines is maintained on the CCR intranet: <https://ccrod.cancer.gov/confluence/display/CCRCRO/Incidental+Findings+Lists>).

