5.4.4 Genetic Counseling

Subjects who remain on the study will be contacted at this time with a request to provide a blood sample to be sent to a CLIA certified laboratory. If the research findings are verified in the CLIA certified lab, the subject will be offered the opportunity to come to NIH (at our expense) to have genetic education and counseling to explain this result. If the subject does not want to come to NIH, a referral to a local genetic healthcare provider will be provided (at their expense).

This is the only time during the course of the study that incidental findings will be returned. No interrogations regarding clinically actionable findings will be made after the primary analysis.

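### Section 12.5.1.9 directs that participants be told genetic data will not be shared with them, without the exception that its third bullet and sections 5.4.3 and 5.4.4 make for actionable variants

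*Combined protocol and SAP*

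**What the plan says.** Section 12.5.1.9 (Non-Physical Risks of Genetic Research) lists three risks.

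- **First bullet, on unwanted information.** It is a direction about what participants hear: "Participants will be clearly informed that the data related to DNA sequencing and genetic analysis is coded, investigational". The same sentence goes on to rule out sharing with participants, relatives and providers: "data related to DNA sequencing and genetic analysis is coded, investigational and will not be shared with participants, family members or health care providers".
- **Second bullet, on release of information.** "Although there are no plans to release results to the participants, family members or health care providers", the risk of release is to be covered in the consent document.
- **Third bullet, on relatives.** Referring back to earlier text, it says that "participants will be notified of any medically significant and actionable incidental findings". It closes: "Study results will not be shared with participants".

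Section 5.4.3 (Management of Results) sets the working rule: "Subjects will be contacted if a clinically actionable gene variant is discovered". It fixes the scope: "Clinically actionable findings for the purpose of this study are defined as disorders appearing in the American College of Medical Genetics and Genomics recommendations" on incidental findings, in the list current at the primary analysis.

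Section 5.4.4 (Genetic Counseling) gives the steps. Participants still on study are asked for a blood sample for a CLIA-certified laboratory. If the finding is verified, they are offered counseling at NIH or referral to a local genetic provider. On timing it says: "This is the only time during the course of the study that incidental findings will be returned".

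**The concern.** The first two bullets carry no exception, and the protocol contains the very return pathway that they deny. The conflict sits in the text that tells investigators how to describe genetic risk. The first bullet answers the risk of receiving unwanted information with an assurance that none will be passed on. Under 5.4.3 and 5.4.4 it can be.

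At stake is the quality of consent. A participant who would rather not learn of a hereditary variant could accept sequencing on the assurance that nothing will come back, and later be contacted with a request for a confirmation sample. No estimate or test in the statistical plan depends on this.

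**Working it through.** No figure is involved, so the check is a comparison of the texts.

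**Step 1. Set the statements side by side.**

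| Place | Are findings returned to participants? | Exception or limit stated |
|---|---|---|
| 12.5.1.9, first bullet | No; nor to relatives or providers | None |
| 12.5.1.9, second bullet | No release planned, same three groups | None |
| 12.5.1.9, third bullet | Actionable incidental findings yes; study results no | Refers back to earlier text |
| 5.4.3 | Yes, by contact | Disorders on the American College of Medical Genetics and Genomics (ACMG) list current at the primary analysis |
| 5.4.4 | Yes, by confirmation sample, then counseling or referral | Participants still on study; one occasion only |

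Two unqualified denials stand against three statements that something is returned.

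**Step 2. Try to reconcile them.** The most favorable reading is that coded research data stay private, while a verified incidental finding is a different thing and is returned. The third bullet fits this, since it treats incidental findings and study results separately. The first two bullets do not, for two reasons.

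- Under 5.4.3 and 5.4.4 the contact comes before the CLIA result. The participant is approached because research sequencing has shown something, and is asked for blood to check it. That already discloses information drawn from the sequencing data, and does so even if the variant is later not verified.
- The second bullet says that release is not planned, whereas 5.4.4 is such a plan. It can also involve a provider, because a participant who does not want to come to NIH is referred to a local one to have the result explained.

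**Step 3. Is the third bullet a separate, wider rule?** Its wording covers any actionable finding, which is looser than the ACMG list. But the sentence refers back, the earlier text on notifying participants is 5.4.3 and 5.4.4, and 5.4.3 defines actionable findings for this study. It is best read as a loosely worded pointer to 5.4.3. That leaves one conflict: the first two bullets against everything else.

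**Step 4. Can the situation arise?** Yes. Section 5.1 lists white-cell DNA sequencing as a control, 5.2.5 describes the same use, and 5.4.1 allows exome sequencing that may look at known cancer-related mutations. A germline variant could therefore be seen. But 5.1 leaves the correlative studies to investigator discretion and available resources, in selected participants, and 5.4.4 contacts only those still on study. The chance of at least one carrier among n sequenced participants is 1 − (1 − p)^n. The documents give neither the number who will be sequenced nor the carrier rate p, so it cannot be evaluated.

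**The case against.** The strongest reply is that 12.5.1.9 only describes risks, that 5.4.3 and 5.4.4 are the operative procedure, and that the third bullet, in the same short list, already agrees with them. A study team would follow the procedure, and the first two bullets can be taken to mean raw research data. Much of this stands. It does not rescue the first two bullets, because they direct what participants are told, and a participant given that message would not have 5.4.4 to correct it.

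A reader might also infer four stronger things that the documents do not support.

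- *Consent has been given on a wrong statement.* The consent form is not among the documents and may already be right. Only the protocol's direction is shown to be wrong.
- *Three incompatible rules exist.* The back-reference in the third bullet makes it a pointer to 5.4.3.
- *An actionable finding would be withheld.* This is unlikely, because the section headed Management of Results requires contact and the third bullet agrees.
- *A finding is sure or likely to occur.* If all 29 planned participants (21 plus 8) were sequenced and 1% to 4% carried a listed variant, the chance of at least one would be 1 − 0.99^29 = 25% to 1 − 0.96^29 = 69%. The carrier rate is an assumption with no support in the documents, sequencing is discretionary, and 29 is reached only if both cohorts pass their first stage. The range is no estimate for this trial.

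**Conclusion.** The contradiction is real and the text is wrong as written. The first two bullets of 12.5.1.9 direct an unqualified assurance that the third bullet and sections 5.4.3 and 5.4.4 make untrue. Participants told this would be misinformed about the risk of receiving unwanted genetic information.

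The direction has no restriction by cohort, so it reaches everyone enrolled, up to the ceiling of 32 in section 10.2. How many would ever be contacted is unknown. Whether anyone has been misinformed depends on the unseen consent form. The conclusion rests on reading the first two bullets as they stand and on treating 5.4.3 and 5.4.4 as the intended policy, which the third bullet supports.

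This is an internal inconsistency about consent. It should be corrected, but it has no bearing on the response rate analysis, the two-stage design or safety monitoring.

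**What to change.** In the first and second bullets of 12.5.1.9, and in the last sentence of the third, say that research results will not be shared except as set out in 5.4.3 and 5.4.4, and describe that exception:

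- participants still on study may be contacted once, at the primary analysis, if a variant meeting the 5.4.3 definition is found;
- they will be asked for a confirmation sample, so they may learn of a possible finding before it is confirmed, including one that is later not verified;
- if a CLIA-certified laboratory verifies it, they will be offered the result with counseling or referral.

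In the third bullet, replace the open-ended scope with findings meeting the 5.4.3 definition. Then check that the consent form says the same.

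The cost is wording in one section and a check of the form. No procedure, sample or visit is added, because 5.4.3 and 5.4.4 already provide for contact, confirmation and counseling. Under the Statement of Compliance the amendment needs IRB approval. If the form also has to change, the IRB decides whether participants who have already consented must consent again.

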12.5.2 Known Potential Benefits

As per Section **12.4** the potential benefit to a participant that goes onto study is a reduction in the bulk of their tumor which may or may not have favorable impact on symptoms and/or survival.

12.5.3 Assessment of Potential Risks and Benefits

Metastatic or refractory/recurrent ONB need improved therapy options. Studies suggest that a portion of ONB PD-L1 expression and presence of an associated inflammatory infiltrate. Thus, ONB may be susceptible to checkpoint inhibition. The information gained from this study will allow us to determine that bintrafusp alfa are tolerated in participants with metastatic or recurrent ONB. Furthermore, additional secondary outcomes will allow us to probe into the possibility of improvement in disease progression with bintrafusp alfa. Lastly, information gained from experimental aims will allow us to potentially improve treatment options in the future.

A number of clinically appropriate strategies to minimize risks to participants have been built into the protocol through the means of inclusion/exclusion criteria, monitoring strategies, and management guidelines.

The potential benefit to a participant that participates in this study is better control of their tumor growth and disease recurrence which may or may not have a favorable impact on symptoms and/or survival.

Potential adverse reactions attributable to the administration of the study drug utilized in this trial are discussed in Section **14.1.2**. All care will be taken to minimize side effects, but they can be unpredictable in nature and severity.

12.6 CONSENT PROCESS AND DOCUMENTATION

The informed consent document will be provided as a physical or electronic document to the participant or consent designee(s) as applicable for review prior to consenting. A designated study investigator will carefully explain the procedures and tests involved in this study, and the associated risks, discomforts and benefits. In order to minimize potential coercion, as much time

as is needed to review the document will be given, including an opportunity to discuss it with friends, family members and/or other advisors, and to ask questions of any designated study investigator. A signed informed consent document will be obtained prior to entry onto the study.

The initial consent process as well as re-consent, when required, may take place in person or remotely (e.g., via telephone or other NIH approved remote platforms used in compliance with policy, including HRPP Policy 303) per discretion of the designated study investigator and with the agreement of the participant/consent designee(s). Whether in person or remote, the privacy of the subject will be maintained. Consenting investigators (and participant/consent designee, when in person) will be located in a private area (e.g., clinic consult room). When consent is conducted remotely, the participant/consent designee will be informed of the private nature of the discussion and will be encouraged to relocate to a more private setting if needed.

Consent will be documented with required signatures on the physical document (which includes the printout of an electronic document sent to participant) or as described below, with a manual (non-electronic) signature on the electronic document. When required, witness signature will be obtained similarly as described for the investigator and participant.

Manual (non-electronic) signature on electronic document:

When a manual signature on an electronic document is used for the documentation of consent at the NIH Clinical Center, this study will use the following to obtain the required signatures:

- Adobe platform (which is not 21 CFR Part 11 compliant); or
- iMedConsent platform (which is 21 CFR Part 11 compliant)

During the consent process, participants and investigators will view individual copies of the approved consent document on screens at their respective locations (if remote consent); the same screen may be used when in the same location, but is not required.

Both the investigator and the subject will sign the document with a hand signature using a finger, stylus or mouse.

Note: Refer to the CCR SOP PM-2, Obtaining and Documenting the Informed Consent Process for additional information (e.g., verification of participant identity when obtaining consent remotely) found at:

<https://ccrod.cancer.gov/confluence/pages/viewpage.action?pageId=73203825>

12.6.1 Consent Process for Adults Who Lack Capacity to Consent to Research Participation

For participants addressed in Section **12.3**, an LAR will be identified consistent with Policy 403 and informed consent obtained from the LAR, as described in Section **12.6**.

13 REGULATORY AND OPERATIONAL CONSIDERATIONS

13.1 STUDY DISCONTINUATION AND CLOSURE

This study may be temporarily suspended or prematurely terminated if there is sufficient reasonable cause. Written notification, documenting the reason for study suspension or termination, will be provided by the suspending or terminating party to study participants, investigator, funding agency, the Investigational New Drug (IND) sponsor and regulatory authorities. If the study is prematurely terminated or suspended, the Principal Investigator (PI)

will promptly inform study participants, the Institutional Review Board (IRB), and sponsor and will provide the reason(s) for the termination or suspension. Study participants will be contacted, as applicable, and be informed of changes to study visit schedule.

Circumstances that may warrant termination or suspension include, but are not limited to:

- Determination of unexpected, significant, or unacceptable risk to participants
- Demonstration of efficacy that would warrant stopping
- Insufficient compliance to protocol requirements
- Data that are not sufficiently complete and/or evaluable
- Determination that the primary endpoint has been met
- Determination of futility

Study may resume once concerns about safety, protocol compliance, and data quality are addressed, and satisfy the sponsor, IRB and as applicable, Food and Drug Administration (FDA).

13.2 QUALITY ASSURANCE AND QUALITY CONTROL

The clinical site will perform internal quality management of study conduct, data and biological specimen collection, documentation and completion. An individualized quality management plan will be developed to describe the site's quality management.

Quality control (QC) procedures will be implemented beginning with the data entry system and data QC checks that will be run on the database will be generated. Any missing data or data anomalies will be communicated to the site(s) for clarification/resolution.

Following written Standard Operating Procedures (SOPs), the monitors will verify that the clinical trial is conducted, and data are generated, and biological specimens are collected, documented (recorded), and reported in compliance with the protocol, International Conference on Harmonisation Good Clinical Practice (ICH GCP), and applicable regulatory requirements (e.g., Good Laboratory Practices (GLP), Good Manufacturing Practices (GMP)).

The investigational site will provide direct access to all trial related sites, source data/documents, and reports for the purpose of monitoring and auditing by the sponsor, and inspection by local and regulatory authorities.

13.3 CONFLICT OF INTEREST POLICY

The independence of this study from any actual or perceived influence, such as by the pharmaceutical industry, is critical. Therefore, any actual conflict of interest of persons who have a role in the design, conduct, analysis, publication, or any aspect of this trial will be disclosed and managed. Furthermore, persons who have a perceived conflict of interest will be required to have such conflicts managed in a way that is appropriate to their participation in the design and conduct of this trial. The study leadership in conjunction with the NCI has established policies and procedures for all study group members to disclose all conflicts of interest and will establish a mechanism for the management of all reported dualities of interest.

13.4 CONFIDENTIALITY AND PRIVACY

Participant confidentiality and privacy is strictly held in trust by the participating investigators, their staff, and the sponsor(s). This confidentiality is extended to cover testing of biological samples and genetic tests in addition to the clinical information relating to participants. Therefore,

the study protocol, documentation, data, and all other information generated will be held in strict confidence. No information concerning the study or the data will be released to any unauthorized third party without prior written approval of the sponsor.

All research activities will be conducted in as private a setting as possible.

The study monitor, other authorized representatives of the sponsor, representatives of the Institutional Review Board (IRB), and/or regulatory agencies may inspect all documents and records required to be maintained by the investigator, including but not limited to, medical records (office, clinic, or hospital) and pharmacy records for the participants in this study. The clinical study site will permit access to such records.

The study participant's contact information will be securely stored at the clinical site for internal use during the study. At the end of the study, all records will continue to be kept in a secure location for as long a period as dictated by the reviewing IRB, Institutional policies, or sponsor requirements.

Study participant research data, which is for purposes of statistical analysis and scientific reporting, will be transmitted to and stored at the National Cancer Institute Center for Cancer Research (NCI CCR). This will not include the participant's contact or identifying information. Rather, individual participants and their research data will be identified by a unique study identification number. The study data entry and study management systems used by the clinical site(s) and by NCI CCR research staff will be secured and password protected. At the end of the study, all study databases will be archived at the NIH.

To further protect the privacy of study participants, a Certificate of Confidentiality has been issued by the National Institutes of Health (NIH). This certificate protects identifiable research information from forced disclosure. It allows the investigator and others who have access to research records to refuse to disclose identifying information on research participation in any civil, criminal, administrative, legislative, or other proceeding, whether at the federal, state, or local level. By protecting researchers and institutions from being compelled to disclose information that would identify research participants, Certificates of Confidentiality help achieve the research objectives and promote participation in studies by helping assure confidentiality and privacy to participants.

